10.5 Study Drug Exposure

10.5.1 Actual Treatment Assignment

The actual treatment assigned to a patient will be the treatment that the patient first received regardless of any dispensing issues at a later visit. For example, if a patient was randomised to the placebo+pembrolizumab group but the patient's first dose in the study was setanaxib+pembrolizumab, they will be assigned as having an actual treatment as the setanaxib+pembrolizumab group they first received, even if they were later dispensed placebo+pembrolizumab at all remaining visits.

10.5.2 Administration Dates

The date of first dose of IMP will be the date recorded on the "Study Drug Administration (IMP)" page of the eCRF for the first non-zero dose. The date of first dose of pembrolizumab will be the date recorded on the "IV/Infusion Administration" page of the eCRF.

Date of last dose of IMP will be the "Completion/Discontinuation Date" on the "End of Treatment (IMP)" page of the eCRF. If date of last dose of IMP is not available because the patient is ongoing at the time of a data cut, then the date of the data cut will be used. If the patient is lost to follow-up (identified via the EoT eCRF page), then the date of the last scheduled visit or the date of last telephone contact where a non-zero dose is recorded, will be used.

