^a Patients who permanently discontinue IMP prior to completion of the 105-week Double-blind Treatment Period will have an EoT Visit as soon as possible and a Safety Follow-up Visit at 28 days after the last IMP dose. Efficacy assessments will continue beyond this 28-day follow-up until disease progression.

- ^b Eligibility to enter the Double-blind Treatment Period will be determined during Visit 1, with a final check before randomisation on Day 1.
- ^c A complete physical examination, including assessments of the standard physical examination items (general appearance, skin, eyes, ears, nose, throat, head and neck, heart, chest and lungs, abdomen, extremities, lymph nodes, musculoskeletal, neurological, and other body systems, if applicable, for describing the status of the patient's health), will be performed during Screening Visit 1 and at the Week 105 Visit (Visit 37). Patients who permanently discontinue IMP prior to or at the Week 105 Visit will have a complete physical examination at the EoT Visit. For Visits 2 to 36, when applicable, a symptoms-directed physical examination will be performed.
- ^d At Visit 2 (Study Day 1) and Visit 3, 12-lead ECG will be recorded pre-dose and 2 hours (± 30 minutes) post setanaxib/placebo dosing. From Visit 4 onwards, 12-lead ECG are only required before setanaxib/placebo dosing; additional ECGs may be recorded as clinically indicated.

• A blood sample for the serum pregnancy test must be taken within 7 days of Day 1 (female patients of childbearing potential only). Therefore, if Screening Visit is performed more than 7 days prior to Day 1, the serum pregnancy test must be repeated within 7 days of Day 1.

Haematology: haematocrit, haemoglobin, absolute and relative reticulocyte counts, RBC count, WBC count, differential WBC count, platelet count, absolute neutrophil count, mean cell volume, and INR (INR only at Screening).

Biochemistry: ALP, ALT, AST, amylase, total and conjugated bilirubin, GGT, glucose, total protein, albumin, creatinine, urea, total cholesterol, triglycerides, sodium, potassium, and chloride.

Thyroid function test: TSH and free T4

- ^g Blood samples for PK assessment will be collected just before the start of pembrolizumab infusion and before the IMP morning dose at Day 1, Week 3, Week 24, Week 51, and Week 105, and PK samples may be collected at any time on the day of the second biopsy and at EoT Visit.

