- ^h Blood samples (20 mL whole blood) will be collected for analysis of exploratory circulating biomarkers before commencing study treatment, during treatment (at Week 9) and at progression.
- ⁱ Qualitative tests will be performed using urine dipsticks.
- ^j Urine pregnancy test, for females of childbearing potential only, will be performed at each visit before dosing.

Table 1Schedule of Assessments

Study Period	Screening		Double-blind Treatment Period		EoTª	Follow-up ^a	
Study Weeks:	-5 to -1	BL	3, 6, 9, 12, 15, 18, 21, 24, 27, 30, 33, 36, 39, 42, 45, 48, 51, 54, 57, 60, 63, 66, 69, 72, 75, 78, 81, 84, 87, 90, 93, 96, 99, 102	105	EoT Visit	Last IMP Dose+28 (±7 days)	Refer to Footnote 'L' ¹
Study Days (Visit Window):	-35 to -1	1	Every 21 days (±5)	735 (±3)			
Visit:	1	2	3 to 36	37	ЕоТ	Safety Follow-up	Efficacy Follow-up

^k A fresh tumour biopsy will be taken during or within 30 days prior to the Screening Period for assessment of tumour biomarkers (CAFs, CD8⁺ TILs, regulatory T-cells, and PD1-L1) and gene expression analysis. A second biopsy of tumour for assessment of tumour biomarkers and gene expression analysis will be performed 9 weeks (±1 week) after the start of study treatment, or earlier if progression occurs before 9 weeks. A third optional tumour biopsy can be performed at disease progression (only for patients who had their second biopsy at 9 weeks, and who consented to having a third sample).

¹ Tumour response will be assessed on CT/MRI scan using RECIST v1.1 at Visit 5 (Week 9 ±1 week), and then every 6 weeks (±1 week) through the first year, and every 9 weeks (±1 week) thereafter until RECIST v1.1-defined disease progression.

^m Tumour assessments will be conducted from the date of randomisation and continue until RECIST v1.1-defined disease progression, irrespective of treatment discontinuation.

ⁿ Survival will be followed until at least 38 progression events.

^o Pembrolizumab 200 mg will be administered intravenously every 3 weeks

^p Setanaxib 800 mg BID or matching placebo will be administered orally (or via either a feeding tube or a percutaneous endoscopic gastrostomy device in case patients are unable to swallow tablets).

^q Prior medication will be recorded during Screening only.

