5.3.2.1 Detection and Management of Anaemia

Particular attention will be given to the detection and management of potential cases of anaemia. In case of Grade \geq 3 severity anaemia, the investigator will instruct the patient to interrupt IMP administration and to return to the study centre within 7 days so that haemoglobin can be retested. If the severity of anaemia is still Grade \geq 3, and if an alternative cause for the anaemia cannot be documented (alternative cause may include the underlying cancer), IMP will not be resumed and will be permanently discontinued. IMP administration will be resumed only if the retest value for haemoglobin is \geq 9 g/dL and an alternative cause for the anaemia can be documented. The patient will continue to be closely monitored (at least weekly) until normalisation of haemoglobin, ie, return to Baseline values.

Anaemia will be reported to the sponsor (or designee) as an AESI, as defined in Section 7.1.5, following the same procedure as for SAEs (Section 7.4).

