6.10 Compliance

The investigator (or designee) will explain the correct use of the IMP to each patient and will check that each patient is following the instructions properly. Patients will document the IMP doses that they take on a patient IMP dosing card.

Compliance will be assessed by counting the returned tablets and will be documented in the source documents and eCRF. Any deviation from the correct use of the IMP will be recorded in the eCRF.

A record of the number of IMP tablets dispensed to and taken by each patient will be maintained and reconciled with IMP and compliance records. The IMP start and stop dates, including dates for IMP interruptions, will also be recorded in the eCRF.

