Treatment with pembrolizumab will continue until: RECIST v1.1-defined disease progression is determined by the investigator (Eisenhauer et al 2009), unacceptable toxicity, or a maximum of 24 months. If progression is suspected, but not confirmed, study treatment may continue until confirmation of radiological progression. Treatment with setanaxib or placebo will continue throughout the period of pembrolizumab therapy. When pembrolizumab is discontinued, blinded study treatment will also be discontinued.

Baseline assessments will be performed on Day 1 (Visit 2). Post-Baseline assessments will be performed every 3 weeks up to pembrolizumab discontinuation. Following permanent IMP discontinuation at any time during the study, patients will undergo an End-of-Treatment (EoT) Visit as soon as possible and a Safety Follow-up Visit at 28 days after the last dose.

Initial tumour imaging is performed within 35 days prior to the date of treatment and will be used as the Baseline scan for the tumour assessments. Tumour assessments will then be conducted from the date of randomisation and continue until RECIST v1.1-defined disease progression, irrespective of treatment discontinuation. Efficacy Follow-up for PFS and survival will continue until approximately 38 progression events have occurred. AEs will be recorded up to 28 days after study treatment discontinuation, while any further anti-cancer medication will be recorded until disease progression.

The primary endpoint is best percentage change in tumour size. A population with measurable disease will be selected to generate the maximum tumour response data. The secondary endpoints related to numbers of CAFs, CD8⁺ TILs, and regulatory T-cells in tumour tissue, and gene expression analysis in tumour tissue will be used to demonstrate the underlying mechanisms of action of setanaxib and support the primary objective.

Safety and tolerability data will be regularly reviewed by an unblinded IDMC, with the first assessment after approximately 12 patients (6 per treatment group) have had the opportunity to complete at least one cycle of pembrolizumab +/- setanaxib, followed by periodic assessments at a frequency defined in the IDMC Charter. The IDMC may recommend changes to the setanaxib dose regimen or study conduct based on the safety data reviews.

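### The SAP dates the last IMP dose from a discontinuation form and the Safety Follow-Up window from EoT, while the protocol counts from the last dose; for patients stopped after an AESI hold the dates can differ by up to about a week

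*SAP*

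**What the plan says.** **Last dose.** SAP 10.5.2 (Administration Dates): "Date of last dose of IMP will be the 'Completion/Discontinuation Date' on the 'End of Treatment (IMP)' page of the eCRF". The same section takes the first dose from the first non-zero dose on the administration page. For patients lost to follow-up it ties the date to dosing as well: "the date of the last scheduled visit or the date of last telephone contact where a non-zero dose is recorded, will be used".

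**Safety Follow-up.** Footnote a of the protocol's Schedule of Assessments says that patients who stop early "will have an EoT Visit as soon as possible and a Safety Follow-up Visit at 28 days after the last IMP dose". The column header of that schedule allows ±7 days around this target. SAP 8.0 agrees: "patients will undergo an End-of-Treatment (EoT) Visit as soon as possible and a Safety Follow-up Visit at 28 days after the last dose". SAP Table 1 (Analysis Visit Windows) instead sets the target at EoT plus 28 days, ±7. SAP 10.4 adds that follow-up visits feed only that one analysis visit.

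**Holds before a permanent stop.** For Grade 3 or higher anaemia, Protocol 5.3.2.1 has the investigator tell the patient to "interrupt IMP administration and to return to the study centre within 7 days so that haemoglobin can be retested". Protocol 5.3.2.2 gives the corresponding rule for TSH of 10 mIU/L or more, with 5 days. In both, whether IMP is resumed is settled after the retest.

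**Data collected.** Protocol 6.10: "The IMP start and stop dates, including dates for IMP interruptions, will also be recorded in the eCRF".

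**The concern.** Two anchors in the SAP can fall later than the last tablet, and they do so in the patients whose safety data matter most here. Anaemia and hypothyroidism are the study's two AESIs. In both pathways tablets stop first, the retest follows, and the decision not to resume comes last. A form date that records the decision, or an EoT visit held at or after it, is later than the last dose actually taken.

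The last-dose date is used in several derivations: duration of exposure (SAP 10.5.3), planned cumulative dose (10.5.5), relative dose intensity (10.5.6), compliance (10.5.7), the concomitant-medication window (10.6) and the treatment-emergent window (10.10.1). The EoT anchor decides which follow-up visits enter the by-visit safety summaries.

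This is not explained by protocol versions. The protocol supplied is version 4.0 and the SAP was written against version 5.0, but SAP 8.0 itself still counts from the last dose. The changes from protocol listed in SAP 6.1 do not mention a new follow-up anchor.

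**Working it through.** The plan gives no figure to reproduce, so the check is day arithmetic.

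**Inputs**
- Protocol window: last dose + 28 ± 7, that is days 21 to 35 after the last tablet (15 allowed days).
- SAP window: EoT + 28 ± 7 (Table 1).
- Hold before the stop decision: up to 7 days for anaemia (Protocol 5.3.2.1), up to 5 for TSH (Protocol 5.3.2.2).
- Planned dose: 800 mg BID = 1600 mg/day.
- Compliance limit: 80% (SAP 10.5.7 and 12.3.1).

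**Definition.** Let g be the days from the last tablet to the SAP's anchor. For exposure, dose intensity and the 28-day windows, the anchor is the form date. For the visit window it is EoT. The two need not be the same day. I take g = 5 or 7, meaning that the anchor is the retest day and the hold runs its full length.

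**Formulas**
- Exposure overstatement = g/7 weeks.
- SAP visit window = days 21 + g to 35 + g after the last tablet.
- End of the 28-day windows = day 28 + g after the last tablet.
- Relative dose intensity under SAP 10.5.6 reduces to cumulative dose / planned cumulative dose × 100, the same ratio as compliance in 10.5.7. With n fully dosed days before the hold, it equals 1600n / [1600(n + g)] = n/(n + g).

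**Windows and exposure**

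| g (days) | Exposure added | SAP follow-up window | On-time days outside it | Day 28 inside? | 28-day windows end |
|---|---|---|---|---|---|
| 0 | 0.0 wk | 21–35 | none | yes | day 28 |
| 5 (TSH) | 0.7 wk | 26–40 | 21–25 (5 of 15) | yes | day 33 |
| 7 (anaemia) | 1.0 wk | 28–42 | 21–27 (7 of 15) | yes | day 35 |
| 8 | 1.1 wk | 29–43 | 21–28 (8 of 15) | no | day 36 |
| 15 | 2.1 wk | 36–50 | all 15 | no | day 43 |

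The last two rows are beyond anything that the hold rules produce. They show only where the target day, and then the whole protocol window, would be lost. The shift works both ways: at g = 7, visits on days 36 to 42, late under the protocol, would count as in window.

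**Relative dose intensity and compliance (true value 100%)**

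| Dosed days n | g = 5 | g = 7 |
|---|---|---|
| 21 | 21/26 = 80.8% | 21/28 = 75.0% |
| 28 | 28/33 = 84.8% | 28/35 = 80.0% |
| 63 | 63/68 = 92.6% | 63/70 = 90.0% |

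At 63 dosed days and g = 7, exposure is reported as 70/7 = 10.0 weeks instead of 63/7 = 9.0. A fully compliant patient falls below the 80% limit only if n/(n + 7) < 0.80, that is, with fewer than 28 dosed days before a full 7-day hold.

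**After the correction.** With both rules anchored on the last non-zero dose, g = 0 and every discrepancy above is zero.

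**The case against.** **The form field may already be the last-dose date.** The eCRF and its completion instructions are not in the documents, and SAP 10.5.2 treats the field as the last dose. If sites enter the date of the last tablet, the exposure, dose-intensity and 28-day-window effects vanish. This stands, and it makes those effects conditional.

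**EoT in Table 1 may not mean the visit.** The glossary expands it only as End of Treatment. If it means the date on the End of Treatment (IMP) page, Table 1 is last dose + 28 in the SAP's own terms. This stands in part: SAP 10.4 uses EoT as a visit label, and Table 1 settles neither reading.

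**A reader might infer that visits on the protocol's target day are dropped.** The documents do not support that. The cited holds are at most 7 days, and day 28 stays inside the SAP window until the gap reaches 8. Only early, on-time visits are exposed. Values outside the window would still be listed, and the rule in SAP 10.4 could be read simply as keeping follow-up visits out of the Week-N windows.

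**Interruptions are counted by design.** SAP 10.5.3 ignores temporary interruptions. But a hold that is never resumed is not temporary, and SAP 10.5.5 runs the planned dose only up to the last dose. This objection does not remove the point.

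**The effect is small.** This stands. The 75% figure needs a short exposure and the longest hold; at 63 dosed days it is 90%. A late treatment-emergent cut-off adds events rather than hiding them.

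**Conclusion.** The point holds as an inconsistency of anchors with a minor effect confined to safety and exposure summaries. Certain from the text: Table 1 is worded differently from the protocol and from SAP 8.0, and the last-dose rule rests on a different kind of record from the first-dose and lost-to-follow-up rules.

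Conditional on the form date, or EoT, recording the decision or visit: up to 1.0 week of extra exposure per patient stopped after a hold, understated dose intensity and compliance, 28-day windows closing up to 7 days late, and early on-time follow-up visits at risk of missing the by-visit summaries. These sizes assume full dosing before the hold and an anchor no later than the retest day. A late EoT visit would widen the gap, but the documents give no basis for its length.

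The documents do not give the number of patients affected. The safety summaries are descriptive, and the primary endpoint and the power statements do not use either date.

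**What to change.** 1. In SAP 10.5.2, define the last IMP dose date as the date of the last non-zero dose, taken from the IMP stop and interruption dates that Protocol 6.10 says are in the eCRF. Name the eCRF page that holds them. Use the End of Treatment (IMP) page date only if that date is missing. Keep the existing rules for ongoing and lost-to-follow-up patients.
2. In SAP Table 1, change the Safety Follow-Up target to last IMP dose + 28 days (±7), matching the protocol and SAP 8.0.

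Cost: two wording changes and a small change to one derivation and one window row. No new data are needed if the stop dates are recorded as Protocol 6.10 states. Which page carries them is not shown in the documents and should be confirmed first.

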10.5.3 Duration of Exposure

The total duration of exposure to treatment will be calculated for each treatment component (IMP and pembrolizumab) regardless of temporary interruptions in administration, and will be expressed in weeks (to 1 decimal place [dp]). Exposure to pembrolizumab will include the 3 weeks after the last infusion date, hence the duration of exposure is defined as;

	Duration of IMD Exposure (Weeks)	_ ((Last Dose Date - First Dose Date)+1)
•	Durution of the Exposure (weeks)	- 7

• Duration of Pembrolizumab Exposure (Weeks) = $\frac{((Last Dose Date - First Dose Date)+22)}{7}$

10.5.4 Number of Doses/Infusions

The total number of administered doses/infusions is defined for each treatment component as the total number of doses/infusions of that component administered to the patient during the treatment period.

10.5.5 Cumulative Dose and Planned Cumulative Dose

Cumulative dose is defined for each treatment component as the sum of all doses of that component administered to the patient during the treatment period.

Planned cumulative dose for a study treatment component is defined as the total dose planned per protocol, up to a patients last dose. The planned cumulative dose will be only used for relative dose intensity and compliance calculations. Planned cumulative dose will not be summarised.

• Planned Cumulative Dose (mg) = Planned Daily Dose(mg) * Duration of Exposure (Days)

10.5.6 Actual and Relative Dose Intensity

Actual dose intensity (ADI) and relative dose intensity (RDI) will be derived for IMP only, for patients with a non-zero duration of exposure. These are defined as;

- $ADI (mg/day) = \left(\frac{Cumulative Dose (mg)}{Duration of IMP Exposure (days)}\right)$
- $RDI(\%) = \left(\frac{ADI}{\left(\frac{Planned Cumulative Dose(mg)}{Duration of IMP Exposure(days)}\right)} + 100$

10.5.7 Treatment Compliance

Compliance will be assessed for the study overall for IMP only, and is calculated as;

• Compliance (%) = $\left(\frac{Cumulative Dose(mg)}{Planned Cumulative Dose(mg)}\right) * 100$

Noncompliance is defined as receiving less than 80% or more than 120% of assigned study drug at any visit.

10.6 Prior, Concomitant and Prohibited Medications

Prior medications are defined as those medications which started prior to the first dose date of IMP. See Section 6.6 of the Protocol for a list of prohibited prior medications.

Concomitant medications will be defined as medications starting prior to but ongoing after the first dose date of IMP, or with a start date on or after the first dose date of the IMP, up to and including 28 days after the last dose date of IMP.

Medications which start prior to the first dose date of IMP and are ongoing at the time of first dose will be summarised as both prior and concomitant medications.

Post Treatment medications are medications that started more than 28 days after the last dose of study medication.

The Sponsor will perform ongoing manual review of all medications, flagging any medication deemed to be prohibited in line with Section 6.8 of the protocol.

10.7 Primary Endpoint

10.7.1 Sum of Diameters (SOD)

Tumour size is defined as the sum of the longest diameters (SOD) of the TLs based upon RECIST assessments. This is based on RECIST TL measurements taken at baseline and at the time point of interest. Whilst the SOD is collected on the Disease Response eCRF page, this will be programmatically derived following RECIST 1.1, as the SOD (longest for non-nodal lesions, short axis for nodal lesions) for all TLs.

10.7.2 Target Lesions Too Small to Measure

If a TL is recorded on the eCRF as "Diameter too small to measure" then a value of 5 mm will be imputed to prevent false responses or progressions.

10.7.3 Scaling of Missing Target Lesions

If a TL is missing, then a scaling rule will be applied to account for this missing data. A worked example is provided in Table 2.

If > 1/3 of TL measurements are missing, then TL response will be NE, unless the SOD of non-missing TL would result in PD (i.e. if using a value of 0 for missing lesions, the sum of diameters has still increased by > 20% or more compared to nadir and the sum of TLs has increased by 5mm from nadir).

If \leq 1/3 of the TL measurements are missing, then the results will be scaled up based on the sizes at the nadir visit to give an estimated SOD and this will be used in calculations. This is equivalent to comparing the visit SOD of the non-missing lesions to the nadir SOD excluding the lesions with missing measurements.

The nadir SOD can be any visit that predates the missing measurement, including a "too small to measure" assessment previously imputed using the rule in Section 10.7.2. A newly imputed SOD can also become the new nadir.

Lesion ID	TL Longest Diameter at Nadir Visit	TL Longest Diameter at Analysis Visit
1	7.2	7.1
2	6.7	6.4
3	4.3	4.0
4	8.6	8.5
5	2.5	Missing (because of Intervention)
SOD	29.3	26

Table 2.Example of Scaling

Lesion 5 has a missing diameter at the follow-up assessment. The sum of lesions 1-4 at the follow-up assessment is 26 mm. The sum of the corresponding lesions at nadir time point is 26.8 mm. Scale up as follows to give an estimated TL SOD;

•
$$TL SOD (mm) = SOD at Nadir * \left(\frac{Sum of Non-Missing Diameters at Follow Up}{Sum of Corresponding Diameters at Nadir}\right) = 29.3 * \left(\frac{26}{26.8}\right)$$

